#### Waiver

The additional correlative research involves reviewing medical records of patients who were treated at the MD Anderson Cancer Center on this trial. The samples which will be used were previously collected on other laboratory trials with signed informed consent. The trials with available samples are: LABO2-152, PA13-0291, PA13-0247, PA11-0852, PA12-1099, PA15-0956. Now that patients have completed treatment phase it would be difficult to obtain additional informed consent. We are requesting a waiver of informed consent and waiver of Authorization to Use and Disclose Protected Health Information for the retrospective portion of this study. A Waiver of Informed Consent and a Waiver of Authorization is requested because the data review and sample analysis involve no additional diagnostic or therapeutic intervention, as well as no direct patient contact. It would be impractical to obtain additional consent from patients because they are no longer in treatment, have died or may be lost to follow-up.

### The Principal Investigator:

- Ensures that biological samples from that subject, if stored at the study site, are immediately identified, disposed of /destroyed, and the action documented
- Ensures the laboratory(ies) holding the samples is/are informed about the withdrawn

consent immediately and that samples are disposed/destroyed, the action documented and the signed document returned to the study site

• Ensures that the subject is informed about the sample disposal.

### 8.3 Other assessments

## **8.3.1 ECOG** performance status

ECOG performance status will be assessed at the times specified in the assessment schedules () based on the following:

- 0 = Fully active; able to carry on all pre-disease performance without restrictions
- 1 = Restricted in physically strenuous activity, but ambulatory and able to carry out work of a light or sedentary nature, for example, light housework or office work
- 2 = Ambulatory and capable of all self-care, but unable to carry out any work activities. Up and about more than 50% of waking hours.
- 3 = Capable of only limited self-care; confined to bed or chair more than 50% of waking hours
- 4 = Completely disabled; cannot carry on any self-care. Totally confined to bed or chair
- 5 = Dead

### 9.0 DISEASE EVALUATION AND METHODS

Imaging performed prior to informed consent may be used as baseline assessment if it was performed within 28 days prior to study drug administration. Scans should be scheduled in such a way that the scan results are available at the regularly scheduled visit.

CT or MRI scans will be performed every 8 weeks for the first 48 weeks and then every 12 weeks until confirmed PD.

Additional imaging may be performed at any time to confirm suspected progression of disease. Study films (abdominopelvic CT/MRI and bone scan) should be read on site. The principal investigator or a sub-investigator will evaluate the images for all subjects for the duration of the study.

The same imaging method used for an individual subjects at baseline should be used throughout the entire study for that subject, unless for medical reasons the method must be changed (e.g. inability to receive contrast agent).

If a subject is unable to return for restaging scans due to symptoms of progressive disease, he may have scans done by a local facility. These scans should be sent to the investigator for review.

PET scans should not be used to determine disease progression.

Radiographic evaluation of metastatic disease is determined separately for soft -tissue and bone disease.

## 9.1 Radiographic disease assessment for soft tissue tumor deposits

## 9.1.1 Definition of measurable and non-measurable tumor deposits

Radiographic disease assessment for soft tissue tumor deposits is based on CT or MRI scan imaging. Soft tissue tumor deposits are described as measurable or non-measurable as defined in RECIST version 1.1:

- To be considered measurable, soft tissue tumor deposits (other than lymph nodes) must be accurately measured in at least one dimension with a minimum size of 10mm by CT or MRI scan (scan slice thickness no greater than 5mm).
- To be considered pathologically enlarged and measurable a lymph node must be ≥15mm in short axis when assessed by CT or MRI scan (scan slice thickness no greater than 5mm).
- All other lesions, including small lesions (longest diameter <10mm or pathological lymph nodes with ≥10 to <15mm short axis) as well as truly non-measurable lesions will be considered non-measurable.

#### 9.1.2 Calculation of tumor burden

- At the baseline tumor assessment, the sum of the products of the two largest perpendicular diameters (Σp-diam) of all index lesions (up to 5 lesions per organ, up to 10 lesions in total that are representative of all involved organs) is calculated and recorded. Non-measurable tumor lesions will be recorded.
- At each subsequent tumor assessment, the Σp-diam of the index lesions and of new, measurable lesions (up to 5 new lesions per organ, up to 10 lesions in total that are representative of all involved organs) are added together to provide the total tumor burden:
  - O Tumor burden= Σp-diam index lesions + Σp-diam new, measurable lesions
- Non-measurable tumor lesions should also be recorded at baseline and at each subsequent tumor assessment.
- At the end of study for that subject, maximum percent reduction from baseline in tumor burden will be graphed

# 9.1.3 Definition of radiographic PD for soft tissue tumor deposits

• An increase in tumor burden of  $\geq$  20% relative to nadir (minimum recorded tumor burden, including the baseline  $\Sigma$ p-diam if that is the smallest on study). In addition to the

relative increase of 20%, the sum must also demonstrate an absolute increase of at least 5 mm.

- In patients classified as having PD within 12 weeks of last tremelimumab dose, confirmation of PD by a second scan ≥ 4 weeks later in the absence of rapid clinical deterioration will be required, as long as the patient does not show other signs or symptoms of disease progression as judged by the investigator.
- The appearance of one or more new lesions (measurable or non-measurable) will not be considered evidence of PD as long as all of the following criteria are met:
  - The increase in tumor burden remains <20% relative to nadir.
  - There are no signs nor symptoms of disease progression (including laboratory parameters, e.g. worsening liver function tests attributable to liver metastases) as judged by the investigator.
  - O There is no further increase in tumor burden observed in a repeat, consecutive assessment obtained  $\geq 4$  weeks later.
  - o For non-measurable tumor lesions an increase in overall disease burden comparable in magnitude to the increase that would be required to declare PD for measurable disease (i.e. ≥20%) will be considered evidence of PD.
  - o If repeat scans confirm PD, then progression should be declared using the date of the initial scan.

## 9.2 Radiographic disease assessment for bone tumor deposits

Radiographic disease assessment for bone lesions is based on standard bone scintigraphy following technetium-99m-MDP injection.

# 9.2.1 Definition of radiographic PD for bone tumor deposits

- Radiographic disease progression for bone lesions is defined as the appearance ≥2 new areas compared to the baseline bone scan that can unequivocally be attributed to prostate cancer (i.e. not attributable to healing or flare of pre-existing lesions).
- Confirmation of PD by a second scan ≥4 weeks later in the absence of rapid clinical deterioration will be required, as long as the patient does not show other signs or symptoms of disease progression as judged by the investigator.
- Equivocal progression on bone scan must be confirmed by other imaging modalities (e.g. CT or MRI) and/or confirmatory bone scan ≥4 weeks later.
- If repeat scans confirm PD, then progression should be declared using the date of the initial scan.

### **9.3 PSA**

Samples for PSA will be collected and analyzed at the treating institution laboratory. PSA testing will be performed as per the schedule of assessment. The PSA test performed at the screening visit does not need to be repeated on C1D1 if visit occurs within 2 weeks of screening.

## 9.4 Definition of progression of disease

For the purposes of this study, progression of disease (PD) is a composite endpoint, consisting of clinical deterioration and/or radiographic progression as defined below. Subjects with PSA progression alone will not be considered to have PD.

### 9.4.1 Clinical deterioration

Clinical deterioration is defined as any symptomatic clinical event attributable to disease progression that, in the investigator's opinion, indicates that the subject is not benefiting from study treatment. Examples include:

- Need for palliative radiation involving more than one site
- Surgery or kyphoplasty to any neoplastic bone lesion
- Cancer associated persistent decrease in performance status (eg, lasting for more than 14 days) of at least 2 points from baseline
- New bladder outlet or ureteral obstruction attributable cancer progression
- Any change of anti-neoplastic therapy for prostate cancer

## 9.4.2 Radiographic progression

Radiographic progression in soft tissue tumor deposits and/or bone as defined in (Sections 9.1.3 and 9.2.1) above will be considered evidence of disease progression.

PSA progression alone will not be used to define progression.

#### 10.0 ASSESSMENT OF SAFETY

The Principal Investigator is responsible for ensuring that all staff involved in the study is familiar with the content of this section.

## **Recommended Adverse Event Recording Guidelines**

Attribution	Grade 1	Grade 2	Grade 3	Grade 4	Grade 5
Unrelated	Phase I	Phase I	Phase I Phase II	Phase I Phase II Phase III	Phase I Phase II Phase III
Unlikely	Phase I	Phase I	Phase I Phase II	Phase I Phase II Phase III	Phase I Phase II Phase III
Possible	Phase I Phase II	Phase I Phase II Phase III			
Probable	Phase I Phase II	Phase I Phase II Phase III			
Definitive	Phase I Phase II	Phase I Phase II Phase III			

## 10.1 Safety Parameters

## 10.1.1 Durvalumab + tremelimumab adverse events of special interest

An adverse event of special interest (AESI) is one of scientific and medical interest specific to understanding of the Investigational Product and may require close monitoring and rapid communication by the investigator to the supporter. An AESI may be serious or non-serious. The rapid reporting of AESIs allows ongoing surveillance of these events in order to characterize and understand them in association with the use of this investigational product.

AESIs for durvalumab and tremelimumab include but are not limited to events with a potential inflammatory or immune-mediated mechanism and which may require more frequent monitoring and/or interventions such as steroids, immunosuppressants and/or hormone replacement therapy. These AESIs are being closely monitored in clinical studies with durvalumab monotherapy and combination therapy. An immune-related adverse event (irAE) is defined as an adverse event that is associated with drug exposure and is consistent with an immune-mediated mechanism of action and where there is no clear alternate aetiology. Serologic, immunologic, and histologic (biopsy) data, as appropriate, should be used to support an irAE diagnosis. Appropriate efforts should be made to rule out neoplastic, infectious, metabolic, toxin, or other etiologic causes of the irAE.

If the Investigator has any questions in regards to an adverse event (AE) being an irAE, the Investigator should promptly contact the Study Physician.

AESIs observed with durvalumab and tremelimumab include:

- Colitis
- Pneumonitis
- ALT/AST increases / hepatitis / hepatotoxicity
- Neuropathy / neuromuscular toxicity (i.e. events of encephalitis, peripheral motor and sensory neuropathies, Guillain-Barré, and myasthenia gravis)
- Endocrinopathy (i.e. events of hypophysitis, adrenal insufficiency, and hyper- and hypothyroidism)
- Dermatitis
- Nephritis
- Pancreatitis (or labs suggestive of pancreatitis increased serum lipase, increased serum amylase)

Further information on these risks (e.g. presenting symptoms) can be found in the current version of the durvalumab and tremelimumab Investigator Brochure. For durvalumab and tremelimumab, AESIs will comprise the following:

#### **Pneumonitis**

AEs of pneumonitis are also of interest for AstraZeneca, as pneumonitis has been observed with use of anti-PD-1 mAbs (but not with anti-PD-L1 mAbs). Initial work-up should include a high-resolution CT scan, ruling out infection, and pulse oximetry. Pulmonary consultation is highly recommended. Guidelines for the management of patients with immune-related AEs (irAEs) including pneumonitis are provided in Table 3.

#### **Infusion reactions**

AEs of infusion reactions (also termed infusion-related reactions) are of special interest to AstraZeneca and are defined, for the purpose of this protocol, as all AEs occurring from the start of IP infusion up to 48 hours after the infusion start time. For all infusion reactions, SAEs should be reported to AstraZeneca Patient safety as described in Table 3.

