## 4.3 Withdrawal of Subjects from Study Treatment and/or Study

#### Permanent discontinuation of either durvalumab plus tremelimumab or durvalumab.

An individual subject will not receive any further investigational product if any of the following occur in the subject in question:

- 1. Withdrawal of consent or lost to follow-up.
- 2. Adverse event that, in the opinion of the investigator or the sponsor, contraindicates further dosing.
- 3. Subject is determined to have met one or more of the exclusion criteria for study participation at study entry and continuing investigational therapy might constitute a safety risk.
- 4. Any AE that meets criteria for discontinuation as defined in the Dosing Modification and Toxicity Management Guidelines (see Table 3).
- 5. Subject noncompliance that, in the opinion of the investigator or sponsor, warrants withdrawal; eg, refusal to adhere to scheduled visits.
- 6. Initiation of alternative anticancer therapy including another investigational agent.
- 7. Confirmation of PD and investigator determination that the subject is no longer benefiting from treatment with durvalumab + tremelimumab.
- 8. Withdrawal of consent from further treatment with IP. The patient is, at any time, free to discontinue treatment, without prejudice to further treatment. A patient who discontinues treatment is normally expected to continue to participate in the study unless they specifically withdraw their consent to further participation in any study procedures and assessments

Subjects who are permanently discontinued from further receipt of investigational product, regardless of the reason (withdrawal of consent, due to an AE, other), will be identified as having permanently discontinued treatment.

Subjects who are permanently discontinued from receiving investigational product will be followed for safety per Section 10.1 and Table 2, including the collection of any protocol-specified blood specimens, unless consent is withdrawn or the subject is lost to follow-up or enrolled in another clinical study. All subjects will be followed for survival. Subjects who decline to return to the site for evaluations will be offered follow-up by phone per the schedule in table 2 as an alternative.

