# 6.2.3 Durvalumab (MEDI4736) + tremelimumab combination therapy dosing schedule

## 6.2.4 Monitoring of dose administration

Patients will be monitored during and after the infusion with assessment of vital signs (blood pressure and pulse) at the times specified in the Study Protocol.

In the event of a ≤Grade 2 infusion-related reaction, the infusion rate of study drug may be decreased by 50% or interrupted until resolution of the event and re-initiated at 50% of the initial rate until completion of the infusion. For patients with a ≤Grade 2 infusion-related reaction, subsequent infusions may be administered at 50% of the initial rate. Acetaminophen and/or an antihistamine (eg, diphenhydramine) or equivalent medications per institutional standard may be administered at the discretion of the investigator. If the infusion-related reaction is ≥Grade 3 or higher in severity, study drug will be discontinued.

As with any antibody, allergic reactions to dose administration are possible. Appropriate drugs and medical equipment to treat acute anaphylactic reactions must be immediately available, and study personnel must be trained to recognize and treat anaphylaxis. The study site must have immediate access to emergency resuscitation teams and equipment in addition to the ability to admit patients to an intensive care unit if necessary

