## 6.3 Dose Modification and Toxicity Management

#### 6.3.1 Durvalumab and tremelimumab

For adverse events (AEs) that are considered at least partly due to administration of durvalumab the following dose adjustment guidance may be applied:

- Treat each of the toxicities with maximum supportive care (including holding the agent suspected of causing the toxicity where required).
- If the symptoms promptly resolve with supportive care, consideration should be given to continuing the same dose of durvalumab or tremelimumab along with appropriate continuing supportive care. If medically appropriate, dose modifications are permitted for durvalumab and tremelimumab (see Table 3).
- All dose modifications should be documented with clear reasoning and documentation of the approach taken.

In addition, there are certain circumstances in which durvalumab or tremelimumab should be permanently discontinued.

Following the first dose of durvalumab or tremelimumab, subsequent administration of durvalumab or tremelimumab can be modified based on toxicities observed. Dose reductions are not permitted.

Based on the mechanism of action of durvalumab or tremelimumab leading to T-cell activation and proliferation, there is the possibility of observing immune related Adverse Events (irAEs) during the conduct of this study. Potential irAEs include immune-mediated enterocolitis, dermatitis, hepatitis, and endocrinopathies. Subjects should be monitored for signs and symptoms of irAEs. In the absence of an alternate etiology (e.g., infection or PD) signs or symptoms of enterocolitis, dermatitis, hepatitis, and endocrinopathy should be considered to be immune-related.

Dose modification recommendations and toxicity management guidelines for immune-mediated reactions, for infusion-related reactions, and for non-immune-mediated reactions are detailed in Table 3.

In addition, management guidelines for adverse events of special interest (AESIs) are detailed in Table 3. All toxicities will be graded according to NCI CTCAE v4.03 other version.

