			
 
GUILLAIN-BARRE:
 
It is important to consider here that the use of steroids as the primary treatment of Guillain-Barre is not typically considered effective.
 

Adverse Events	Severity Grade of the Event (NCI CTCAE	Dose Modifications	Toxicity Management
	version 4.03)		
 
Patients requiring treatment should be started with IV IG and followed by plasmapheresis if not responsive to IV IG.
 

<sup>a ASCO Educational Book 2015 "Managing Immune Checkpoint Blocking Antibody Side Effects" by Michael Postow MD.

AChE Acetylcholine esterase; ADL Activities of daily living; AE Adverse event; ALP Alkaline phosphatase test; ALT Alanine aminotransferase; AST Aspartate aminotransferase; BUN Blood urea nitrogen; CT Computed tomography; CTCAE Common Terminology Criteria for Adverse Events; ILD Interstitial lung disease; irAE Immune-related adverse event; IG Immunoglobulin; IV Intravenous; GI Gastrointestinal; LFT Liver function tests; LLN Lower limit of normal; MRI Magnetic resonance imaging; NCI National Cancer Institute; NCCN National Comprehensive Cancer Network; PCP; PO By mouth; T3 Triiodothyronine; T4 Thyroxine; TB Total bilirubin; TNF Tumor necrosis factor; TSH Thyroid-stimulating hormone; ULN Upper limit of normal.

b FDA Liver Guidance Document 2009 Guidance for Industry: Drug Induced Liver Injury – Premarketing Clinical Evaluation.

Severity Grade of the Event (NCI CTCAE version 4.03)	Dose Modifications	Toxicity Management
Any Grade	General Guidance	For Any Grade:  - Manage per institutional standard at the discretion of investigator.  - Monitor patients for signs and symptoms of infusion-related reactions (eg, fever and/or shaking chills, flushing and/or itching, alterations in heart rate and blood pressure, dyspnea or chest discomfort, or skin rashes) and anaphylaxis (eg, generalized urticaria, angioedema, wheezing, hypotension, ortachycardia).
Grade 1 or 2	For Grade 1:  The infusion rate of study drug/study regimen may be decreased by 50% or temporarily interrupted until resolution of the event.	
 
For Grade 1 or 2:
 
Acetaminophen and/or antihistamines may be administered per institutional standard at the discretion of theinvestigator.
 
Consider premedication per institutional standard prior to subsequent doses.
 

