	For Grade 2:  The infusion rate of study drug/study regimen may be decreased 50% or temporarily interrupted until resolution of theevent.  Subsequent infusions may be given at 50% of the initial infusion rate.	
 
Steroids should not be used for routine premedication of Grade ≤ infusion reactions.
 

Grade 3 or 4	For Grade 3 or 4:  Permanently discontinue study drug/study regimen.	For Grade 3 or 4:  - Manage severe infusion-related reactions per institutional standards (eg, IM epinephrine, followed by IV diphenhydramine and ranitidine, and IV glucocorticoid).

CTCAE Common Terminology Criteria for Adverse Events; IM Intramuscular; IV Intravenous; NCI National Cancer Institute.

Severity Grade of the Event (NCI CTCAE version 4.03)	Dose Modifications	Toxicity Management  Treat accordingly, as per institutional standard.		
Any Grade	Note: Dose modifications are not required for AEs not deemed to be related to study treatment (ie, events due to underlying disease) or for laboratory abnormalities not deemed to be clinically significant.			
Grade 1 No dose modifications.		Treat accordingly, as per institutional standard.		
Grade 2	Hold study drug/study regimen until resolution to ≤Grade 1 or baseline.	Treat accordingly, as per institutional standard.		
Grade 3	Hold study drug/study regimen until resolution to ≤Grade 1 or baseline.	Treat accordingly, as per institutional standard.		
	For AEs that downgrade to ≤Grade 2 within 7 days or resolve to ≤Grade 1 or baseline within 14 days, resume study drug/study regimen administration. Otherwise, discontinue study drug/study regimen.			
Grade 4	Discontinue study drug/study regimen (Note: For Grade 4labs, decision to discontinue should be based on accompanying clinical signs/symptoms, the Investigator's clinical judgment, and consultation with the Sponsor.).	Treat accordingly, as per institutional standard.		

Note: As applicable, for early phase studies, the following sentence may be added: "Any event greater than or equal to Grade 2, please discuss with Study Physician." AE Adverse event; CTCAE Common Terminology Criteria for Adverse Events; NCI National Cancer Institute.

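### The Grade 3 stop for infusion-related reactions rests on a timing-only definition, so as written it also catches unrelated events and events that Table 3 only holds

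*Combined protocol and SAP*

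**What the plan says.** Section 10.1.1 (Infusion reactions) states that infusion reactions are also called infusion-related reactions. For the protocol's purposes it defines them "as all AEs occurring from the start of IP infusion up to 48 hours after the infusion start time".

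Two places act on that term:

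- Section 6.2.4: "If the infusion-related reaction is ≥Grade 3 or higher in severity, study drug will be discontinued". For Grade 2 or lower, "the infusion rate of study drug may be decreased by 50% or interrupted until resolution of the event".
- Table 3, infusion panel, Grade 3 or 4: "Permanently discontinue study drug/study regimen".

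Section 4.3, item 4, makes the Table 3 criteria binding. It lists among the reasons for ending all dosing: "Any AE that meets criteria for discontinuation as defined in the Dosing Modification and Toxicity Management Guidelines".

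Other parts of Table 3 treat some of the same events differently. The non-immune panel says that events judged unrelated to study treatment need no dose change. Several panels hold treatment at Grade 3 and allow it to resume.

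**The concern.** Section 10.1.1 gives an explicit protocol definition, and the stop rules use the defined term without narrowing it. A reader who applies the text literally must end treatment for any Grade 3 or higher adverse event that starts within 48 hours of an infusion. A reader who takes the term in its clinical sense would not. The same event can therefore lead to two different dosing decisions.

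Permanent discontinuation is the largest dosing consequence in the plan. The initial course runs to 13 doses (Section 6.2.1), so the window can open up to 13 times per patient. A stop after dose 1 also makes the patient non-evaluable for the secondary objectives. Section 4.4 requires two combination doses for evaluability and leaves room for only 7 such patients within the maximum of 27.

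**Working it through.** This is a check of text against text. The plan states no figure to reproduce.

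**Step 1. What falls inside the definition.** The only test is timing. The recording table in Section 10.0 includes Grade 3 and higher events in Phase II even when unrelated, so unrelated events are among the adverse events captured. Events unequivocally due to progression are not reported as adverse events (Sections 10.2 and 10.5.4) and are outside this point.

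**Step 2. What the stop rules add.** Neither Section 6.2.4 nor the Grade 3 or 4 row of the infusion panel adds a condition on cause, a list of qualifying signs, or an exception for events with their own panel.

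**Step 3. The same event under its own rule.** Suppose each event starts within 48 hours of an infusion. The literal infusion rule is a permanent stop in every row.

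- Unrelated Grade 3 event, for example a fracture from a fall. Own rule (non-immune panel note): no dose change.
- Related non-immune Grade 3 event, for example fatigue. Own rule: hold, then resume if it falls to Grade 2 or lower within 7 days, or to Grade 1 or baseline within 14 days.
- Endocrinopathy other than hypothyroidism, Grade 3 or 4. Own rule: hold until controlled, then resume.
- Hepatitis, Grade 3, transaminases up to 8 x ULN or bilirubin up to 5 x ULN. Own rule: hold, and resume if recovered within 14 days. Above those limits the panel stops treatment, so there is no conflict there.
- Rash, neurotoxicity and peripheral neuromotor syndromes, Grade 3. Own rule: hold, with a stop if there is no recovery within 30 days. For the neuromotor syndromes, respiratory insufficiency or autonomic instability also stops treatment.
- Asymptomatic amylase or lipase rise, Grade 3 or higher. Own rule: hold, and resume if work-up shows no pancreatitis.
- Pneumonitis, enterocolitis and nephritis, Grade 3. Own rule: stop. No conflict.

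Of the 8 immune panels, 3 stop at Grade 3 and 5 hold first, hepatitis only within its limits. The documents do not say which panel prevails when two apply.

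**Step 4. Scale.** A 28-day cycle has 28 x 24 = 672 hours. The window covers 48/672 = 7.1% of it. On combination days the two infusions start about 2 hours apart, which gives 50/672 = 7.4%. This is a share of calendar time, not of events. The documents give no rate of Grade 3 or higher events starting within 48 hours of an infusion, so the number of patients cannot be derived.

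**Step 5. Does it reach the analyses?** The extreme toxicity definition in Section 11.2.1 has its own requirement that the event be at least possibly related to therapy. It does not use the infusion-reaction term, so Tables 4 and 5 do not depend on it. The final tabulation in Section 11.2.1 is by CTCAE name and worst grade, so it does not use the term either.

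**The case against.** The strongest reply is that the context shows a clinical reaction was meant.

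- The row that orders the stop also recommends epinephrine, antihistamine and glucocorticoid, which is treatment for an acute severe reaction.
- The Any Grade row describes "signs and symptoms of infusion-related reactions (eg, fever and/or shaking chills, flushing and/or itching" and similar signs.
- The rate-reduction steps make no sense for an event 40 hours later, when no infusion is running.
- The title of Table 3 separates immune-mediated, infusion-related and non-immune reactions, and a pure timing reading would erase those classes inside the window.
- The text on immune-related events assigns inflammatory events without another clear cause to the immune panels.
- The section that holds the definition concerns events that "may require close monitoring and rapid communication by the investigator to the supporter", and the definition itself is followed only by an instruction on serious adverse event reporting.
- Section 6.3.1 opens: "For adverse events (AEs) that are considered at least partly due to administration of durvalumab the following dose adjustment guidance may be applied".

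Most of this stands as evidence of intent, and it supports expecting little practical harm. It does not replace the definition. The sign list is given as examples under monitoring advice. The Section 6.3.1 sentence is permissive, names only durvalumab in its condition, and does not govern Section 6.2.4. The hypersensitivity text in Section 10.1.1 sends infusion-related reactions to Table 3, so the defined term does reach the stop rule. The sign list also includes skin rashes and dyspnea, so a drug-related Grade 3 rash could fit both the infusion panel and the rash panel even on a clinical reading.

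One caution also stands. In the public text the infusion and non-immune panels show no title rows, and the last line of Appendix 5 mentions footnotes to the toxicity guidelines that do not appear there. A limiting footnote would answer the point.

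A reader might go further and infer that the sponsor intends to stop treatment for every Grade 3 event in the window, that many patients would be lost, or that the safety monitoring is distorted. The documents support none of these. The context points to a narrower intent, no event rate is given, and the monitoring rule has its own relatedness test. Nor is 5 of 8 panels a measure of size, because it counts panels and not patients.

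**Conclusion.** Wrong as written; minor. The definition is by timing alone, and the Grade 3 or higher stop uses it without a clinical or relatedness limit. Applied literally, the rule permanently stops treatment for unrelated events that other text exempts and for related events that other text only holds. The likely intent is narrower, and many investigators would probably apply it that way.

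The effect is on individual dosing decisions and, after a stop at dose 1, on evaluability. The number affected is expected to be low but cannot be estimated. The conclusion assumes that no footnote missing from the public text limits the infusion panel.

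**What to change.** Keep the 48-hour window in Section 10.1.1, and state that it serves surveillance and serious adverse event reporting only. Add to Section 6.2.4 and to the Table 3 infusion panel:

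*For dosing decisions, an infusion-related reaction is an AE in this window that the investigator judges to be a reaction to the infusion itself, with signs such as those listed in the infusion panel of Table 3; Grade 3 or higher stops study drug. Any other AE in the window follows the Table 3 panel for its event type, and AEs not related to study treatment need no dose change.*

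A simpler condition, that the event be related to either study drug, would not be enough. It would still stop related non-immune Grade 3 events such as fatigue. A blanket exception for events with an immune panel would err the other way, because it could move a true Grade 3 infusion rash to a panel that only holds treatment.

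The cost is a few sentences of text, with no new data collection and no change to serious adverse event capture. The downside is reliance on investigator attribution in an open-label trial. Section 10.2 already records causality against the study drugs for every adverse event, and the extreme toxicity rule already depends on attribution. The yes/no causality rating does not itself separate an infusion reaction from another drug-related event, so the reason for any stop should be written down, as Section 6.3.1 already asks for dose modifications.
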